**Lab Test = Sodium**

CTCAE Term	Grade 1	Grade 2	Grade 3	Grade 4	Grade 5
Hypernatremia	>ULN - 150 mmol/L	>150 - 155 mmol/L; intervention initiated	>155 - 160 mmol/L; hospitalization indicated	>160 mmol/L; life-threatening consequences	Death
Hyponatremia	<LLN - 130 mmol/L	125-129 mmol/L and asymptomatic	125-129 mmol/L symptomatic; 120-124 mmol/L regardless of symptoms	<120 mmol/L; life-threatening consequences	Death

Hypernatremia will have grades 1-4,

- Grade 1 being any values from the ULN to 150 mmol/L,
- Grade 2 from >150 to 155 mmol/L,
- Grade 3 from >155 to 160 mmol/L,
- Grade 4 from >160 mmol/L

Hyponatremia will have grades 1-4,

- Grade 1 being any values from the LLN to 130 mmol/L,
- Grade 2 from 125 to <130 mmol/L,
- Grade 3 from 120 to <125 mmol/L,
- Grade 4 <120 mmol/L

**Lab Test = Triglycerides**

CTCAE Term	Grade 1	Grade 2	Grade 3	Grade 4	Grade 5
Hypertriglyceridemia	150 mg/dL - 300 mg/dL; 1.71 mmol/L - 3.42 mmol/L	>300 mg/dL - 500 mg/dL; >3.42 mmol/L - 5.7 mmol/L	>500 mg/dL - 1000 mg/dL; >5.7 mmol/L - 11.4 mmol/L	>1000 mg/dL; >11.4 mmol/L; life-threatening consequences	Death

Triglycerides will have grades 1-4,

- Grade 1 being any values from the 150 to 300 mg/dL,
- Grade 2 from >300 to 500 mg/dL,
- Grade 3 from >500 to 1000 mg/dL,
- Grade 4 from >1000 mmol/L

**Lab Test = Uric Acid**

CTCAE Term	Grade 1	Grade 2	Grade 3	Grade 4	Grade 5
Hyperuricemia	>ULN without physiologic consequences	-	>ULN with physiologic consequences	Life-threatening consequences	Death

- Do not grade based on CTCAE

**Lab Test = Bicarbonate or CO2**

CTCAE Term	Grade 1	Grade 2	Grade 3	Grade 4	Grade 5
Blood bicarbonate decreased	<LLN and no intervention initiated	-	-	-	-

Do not Grade based on CTCAE

**Lab Test = Phosphorus or Phosphate**

CTCAE Term	Grade 1	Grade 2	Grade 3	Grade 4	Grade 5
Hypophosphatemia	Laboratory finding only and intervention not indicated	Oral replacement therapy indicated	Severe or medically significant but not immediately life-threatening; hospitalization or prolongation of existing hospitalization indicated	Life-threatening consequences	Death
Hyperphosphatemia	Laboratory finding only and intervention not indicated	Noninvasive intervention indicated	Severe or medically significant but not immediately life-threatening; hospitalization or prolongation of existing hospitalization indicated	Life-threatening consequences; urgent intervention indicated (e.g., dialysis)	Death

Do not Grade based on CTCAE

**Lab Test = Serum pH [This is not urine pH]**

CTCAE Term	Grade 1	Grade 2	Grade 3	Grade 4	Grade 5
Acidosis	pH <normal, but >=7.3	-	pH <7.3	Life-threatening consequences	-
Alkalosis	pH >normal, but <=7.5	-	pH >7.5	Life-threatening consequences	-

Serum pH will be graded in both directions with Grades 1 and 3 only.

Acidosis Grade 1 .<LLN, but >=7.3 Grade 3, pH < 7.3

Alkaosis Grade 1 .>ULN, but <=7.5 Grade 3, pH < 7.5

**Lab Test = Activated Partial Thromboplastin Time**

CTCAE Term	Grade 1	Grade 2	Grade 3	Grade 4	Grade 5
Activated partial thromboplastin time prolonged	>ULN - 1.5 x ULN	>1.5 - 2.5 x ULN	>2.5 x ULN; bleeding	-	-

APTT will have grades 1-3

- Grade 1 being any values from the >ULN to 1.5 x ULN,
- Grade 2 from >1.5 to 2.5 x ULN,
- Grade 3 from >2.5 x ULN,

**Lab Test = International Normalized Ratio**

CTCAE Term	Grade 1	Grade 2	Grade 3	Grade 4	Grade 5
INR increased	>1.2 - 1.5; >1 - 1.5 x baseline if on anticoagulation; monitoring only indicated	>1.5 - 2.5; >1.5 - 2.5 x baseline if on anticoagulation; dose adjustment indicated	>2.5; >2.5 x baseline if on anticoagulation; bleeding	-	-

INR will have grades 1-3

- Grade 1 being any values from the >1.2 to 1.5,
- Grade 2 from >1.5 to 2.5,
- Grade 3 from >2.5,

**Lab Test = Eosinophils**

CTCAE Term	Grade 1	Grade 2	Grade 3	Grade 4	Grade 5
Eosinophilia	>ULN and >Baseline	-	Steroids initiated	-	-

Do not grade based on CTCAE

**Lab Test = Hemoglobin**

CTCAE Term	Grade 1	Grade 2	Grade 3	Grade 4	Grade 5
Anemia	Hemoglobin (Hgb) <LLN - 10.0 g/dL; <LLN - 6.2 mmol/L; <LLN - 100 g/L	Hgb <10.0 - 8.0 g/dL; <6.2 - 4.9 mmol/L; <100 - 80g/L	Hgb <8.0 g/dL; <4.9 mmol/L; <80 g/L; transfusion indicated	Life-threatening consequences; urgent intervention indicated	Death
Hemoglobin Increased	Increase in > 0-2	Increase in >2-4g/dL	Increase > 4 g/DL	-	Death

Decreased Hemoglobin will have grades 1-3, with

- Grade 1 being any values from the LLN to 10 g/dL,
- Grade 2 from 8 to < 10 g/dL and
- Grade 3 < 8 g/dL

Increased Hemoglobin will not be graded.

**Lab Test = CD4 Lymphocytes**

CTCAE Term	Grade 1	Grade 2	Grade 3	Grade 4	Grade 5
CD4 lymphocytes decreased	<LLN - 500/mm  ; <LLN - 0.5 x 10  /L	<500 - 200/mm  ; <0.5 - 0.2 x 10  /L	<200 - 50/mm  ; <0.2 x 0.05 - 10  /L	<50/mm  ; <0.05 x 10  /L	-

Decreased CD4 count will have grades 1-4, with

- Grade 1 being any values from the LLN to 500/mm^3,
- Grade 2 from <500 to 200/mm^3 and
- Grade 3 from <200 to 50/mm^3 and
- Grade 4 <50/mm^3

**Lab Test = Lymphocytes**

CTCAE Term	Grade 1	Grade 2	Grade 3	Grade 4	Grade 5
Lymphocyte count decreased	<LLN - 800/mm  ; <LLN - 0.8 x 10  /L	<800 - 500/mm  ; <0.8 - 0.5 x 10  /L	<500 - 200/mm  ; <0.5 - 0.2 x 10  /L	<200/mm  ; <0.2 x 10  /L	Lymphocyte count decreased
Lymphocyte count increased	-	>4000/mm  - 20,000/mm 	>20,000/mm 	-	Lymphocyte count increased

Lymphocytes will be graded in both directions.

Decreased Lymphocytes will have grades 1-4, with

- Grade 1 being any values from the LLN to 800/mm^3,
- Grade 2 from <800 to 500/mm^3 and
- Grade 3 from <500 to 200/mm^3 and
- Grade 4 <200/mm^3

Increase Lymphocytes will have grades 2 and 3 only, with

- Grade 2 from >4000 to 20,000/mm^3 and
- Grade 3 >20,000/mm^3

**Lab Test = Neutrophils**

CTCAE Term	Grade 1	Grade 2	Grade 3	Grade 4	Grade 5
Neutrophil count decreased	<LLN - 1500/mm  ; <LLN - 1.5 x 10  /L	<1500 - 1000/mm  ; <1.5 - 1.0 x 10  /L	<1000 - 500/mm  ; <1.0 - 0.5 x 10  /L	<500/mm  ; <0.5 x 10  /L	-

Neutrophils will have grades 1-4, with

- Grade 1 being any values from the LLN to 1500/mm^3,
- Grade 2 from 1000 to <1500/mm^3 and
- Grade 3 from 500 to <1000/mm^3 and
- Grade 4 <500/mm^3

**Lab Test = Platelets**

CTCAE Term	Grade 1	Grade 2	Grade 3	Grade 4	Grade 5
Platelet count decreased	<LLN - 75,000/mm  ; <LLN - 75.0 x 10  /L	<75,000 - 50,000/mm  ; <75.0 - 50.0 x 10  /L	<50,000 - 25,000/mm  ; <50.0 - 25.0 x 10  /L	<25,000/mm  ; <25.0 x 10  /L	-

Do not grade with CTCAE.

## Lab Test = WBC

CTCAE Term	Grade 1	Grade 2	Grade 3	Grade 4	Grade 5
White blood cell decreased	<LLN - 3000/mm  ; <LLN - 3.0 x 10  /L	<3000 - 2000/mm  ; <3.0 - 2.0 x 10  /L	<2000 - 1000/mm  ; <2.0 - 1.0 x 10  /L	<1000/mm  ; <1.0 x 10  /L	-
Leukocytosis	-	-	>100,000/mm 	Clinical manifestations of leucostasis; urgent intervention indicated	Death

Decreased WBC will have grades 1-4, with

- Grade 1 being any values from the LLN to 3000/mm^3,
- Grade 2 from 2000 to <3,000/mm^3 and
- Grade 3 from 1000 to <2,000/mm^3 and
- Grade 4 <1000/mm^3

High WBC will have grade 1, with

- Grade 1 >11,000/mm^3 (<https://www.aafp.org/afp/2000/1101/p2053.html>).

**Lab Test = Urine Glucose**

CTCAE Term	Grade 1	Grade 2	Grade 3	Grade 4	Grade 5
Glucosuria	Present	-	-	-	-

Urine Glucose will have grade 1

- Grade 1 if not negative or trace

**Lab Test = Urine Protein**

CTCAE Term	Grade 1	Grade 2	Grade 3	Grade 4	Grade 5
Proteinuria	1+ proteinuria; urinary protein $\geq$ ULN - $<1.0$ g/24 hrs	Adult: 2+ and 3+ proteinuria; urinary protein 1.0 - $<3.5$ g/24 hrs;  Pediatric: Urine P/C (Protein/Creatinine) ratio 0.5 - 1.9	Adult: Urinary protein $\geq=3.5$ g/24 hrs; 4+ proteinuria;  Pediatric: Urine P/C (Protein/Creatinine) ratio $>1.9$	-	-

Urine Protein will have grades 1-3, with

- Grade 1 =1+
- Grade 2 = 2+ to 3+
- Grade 3 = 4+

**Lab Test: Urine RBCs/Blood**

CTCAE Term	Grade 1	Grade 2	Grade 3	Grade 4	Grade 5
Hematuria	Asymptomatic; clinical or diagnostic observations only; intervention not indicated	Symptomatic; urinary catheter or bladder irrigation indicated; limiting instrumental ADL	Gross hematuria; transfusion, IV medications, or hospitalization indicated; elective invasive intervention indicated; limiting self care ADL	Life-threatening consequences; urgent invasive intervention indicated	Death

Do not grade urine in blood using CTCAE

**Lab Test: eGFR or CrCl**

CTCAE Term	Grade 1	Grade 2	Grade 3	Grade 4	Grade 5
eGFR decreased/CrCl decreased	eGFR (estimated Glomerular Filtration Rate) or CrCl (creatinine clearance) <LLN - 60 ml/min/1.73 m  or proteinuria 2+ present; urine protein/creatinine >0.5	eGFR or CrCl 59 - 30 ml/min/1.73 m 	eGFR or CrCl 29 - 15 ml/min/1.73 m 	eGFR or CrCl <15 ml/min/1.73 m  ; dialysis or renal transplant indicated	Death

Values will be graded using the CTCAE values noted above with Grade 1 – Grade 4 values.

eGFR/CrCl:

Grade 1: < LLN – 60 ml/min/1.73 m^2

Grade 2: 30 - < 60 ml/min/1.73 m^2

Grade 3: 15 - < 30 ml/min/1.73 m^2

Grade 4: < 15 ml/min/1.73 m^2

## 9.4. Programming Conventions

- Page orientation, margins, and fonts: Summary tables, listings, and figures will appear in landscape orientation. There should be a 1.0" boundary on the left and right edges. The top and bottom margins are 1.0" for tables and listings but may vary for figures. Output should be printed in Courier New with a point size of 8.
- Identification of analysis population: Every summary table, listing, and figure will clearly specify the analysis population being summarized/listed. Listings will be prepared for all subjects.
- Group headers: In the summary tables, the group headers will identify the within-group sample size for the indicated analysis population. Of note, the header's sample size does not necessarily equal the number of subjects actually summarized within any given summary module; some subjects in the analysis population may have missing values and thus may not be summarized.
- Suppression of percentages corresponding to null categories: When count data are presented as category frequencies and corresponding percentages, the percent should be suppressed when the count is zero in order to draw attention to the non-zero counts.
- Presentation of sample sizes: Summary modules should indicate, in one way or another, the number of subjects actually contributing to the summary statistics presented in any given summary module. As mentioned above, this may be less than the number of subjects in the analysis population.
  - In the quantitative modules describing continuous variables (and thus presenting sample size, means, and standard deviations), the sample size should be the number of non-missing observations
  - For categorical variables that are presented in frequency tables, the module should present the total count in addition to the count in each category. Percentages should be calculated using this total as the denominator, and the percentage corresponding to the sum itself (that is, 100%) should be presented so as to indicate clearly to a reviewer the method of calculation.
- Sorting: Listings will be sorted by treatment, subject number and date, if applicable. If a listing is sorted in a different manner, it will be indicated on the listing shells.
- General formatting rules: Rounding for all variables will occur only as the last step, immediately prior to presentation in listings, tables, and figures. No intermediate rounding will be performed on derived variables. The standard rounding practice of rounding numbers ending in 0-4 down and numbers ending in 5-9 up will be employed.
- The presentation of numerical values will adhere to the following guidelines:
  - Raw measurements will be reported to the number of decimal places as captured electronically or on the eCRFs.
  - Minimums and maximums will be reported to the number of decimal places the original parameter is presented

- Standard deviations will be reported to two decimal places beyond the number of decimal places the original parameter is presented.
- Means and quartiles will be reported to the one decimal place beyond the number of decimal places the original parameter is presented.
- Calculated percentages will be reported with one decimal place.
- Coefficient of variation will be reported to the same number of decimal places as the standard deviation.
- In some cases, when the raw measurements are calculated values with 3 or more decimal places, the above guideline may be adjusted for readability
- Dates will be formatted as DDMMYY. Partial dates will be presented on data listings as recorded on eCRFs.
- Time will be presented according to the 24-hour clock (HH:MM).
- Verification of Results: All analyses will be subject to formal verification procedures. Specifically, results will be verified utilizing independent programming prior to issuance of the draft statistical report. All documents will be verified by the lead statistician to ensure accuracy and consistency of analyses.

## 9.6. Core Codes for Imputation of MAR and MNAR

### 9.6.1. Imputation of Missing at Random (MAR) Cases

SAS PROC MI will be used to generate 25 possible imputed datasets using the following SAS code:

```
proc mi data=mcmc1 seed=SEED1 nimpute=25 out=Out1X;
mcmc chain=multiple displayinit initial=em(itprint);
var TRT Y0 Y1 Y2 ... Yn;
run;
```

Here, TRT is an indicator variable representing treatment with values of 'Emraclidine' or 'Placebo', Y1 - YN are variables representing the response variable (e.g., PANSS total score or CGI-S severity score) for each visit, Y0 is the baseline score, and SEED1 is a random number.

Each of these datasets will be analyzed using PROC MIXED in SAS using the MMRM model. The results of the analyses of the datasets will be combined using PROC MIANALYZE to produce an inferential result.

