### 9.6.2. Imputation of Missing Not at Random (MNAR) Cases

The MNAR cases will be imputed using a tipping point analysis. Subjects identified in [Section 9.5](#) who were treated with values of 'Emraclidine' will have their imputed values that occurred following an ICE shifted by delta. Delta will be defined based on a percentage (10%-90%) of the mixed effect repeated measures model least-square means difference estimate at each visit relative to each 'Emraclidine' arm from the primary endpoint analysis.

First, the SAS code in [Section 9.6.1](#) will be used to generate 25 possible imputed datasets using PROC MI. Then, the delta shift will be applied to these imputed datasets using the code below:

```
data ShiftX;
set Out1X;
if CRIT1FL = 'Y' and DCSRELFL = 'Y' and TRT ^= 'Placebo' then do;
  if AVISITN > VISITN then do;
    AVAL = AVAL0 + DELTA;
    if AVAL > MAX then AVAL = MAX
    if missing < AVAL < MIN then aval = MIN;
    if ABLFL ^= 'Y' then CHG = AVAL - BASE;
  end;
run;
```

Here, TRT is an indicator variable representing treatment with values of 'Placebo' excluded from the delta adjustment, CRIT1FL is an indicator variable representing imputed records with values

of 'Y' indicating a record was imputed, DCSRELEF is an indicator variable representing type of missingness with values of 'Y' indicating an MNAR case, AVISITN is a variable representing the analysis visit, VISITN is a variable representing the subject's last visit prior to the ICE, AVAL0 is a variable representing the original imputed value for the response variable (e.g., PANSS total score or CGI-S severity score) prior to the delta shift, DELTA is a variable representing the shift applied to each imputed value for subjects with treatment values of 'Emraclidine' that occurred after a subject's ICE, AVAL is a variable representing the new value for the response variable following the delta shift, MAX is a variable representing the maximum possible value for the response variable (e.g., 210 for PANSS total score), MIN is a variable representing the minimum possible value for the response variable (e.g., 30 for PANSS total score), ABLFL is an indicator variable flagging the visit that represents the subject's baseline value, BASE is a variable representing the baseline value for the response variable, and CHG is a variable representing the new calculated response variable based on BASE and AVAL.

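### With 25 imputations and a placeholder seed, a borderline multiple-imputation or tipping-point sensitivity result for PANSS or CGI-S can change with the random seed; H1-H4 are not affected

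*SAP*

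**What the plan says.** SAP 5.9.3.2 plans multiple imputation under MAR with 25 datasets, followed by a pattern-mixture tipping-point analysis for discontinuations treated as MNAR. SAP 5.10.3 applies both to CGI-S.

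SAP 9.6.1 states "SAS PROC MI will be used to generate 25 possible imputed datasets using the following SAS code", and the code is "proc mi data=mcmc1 seed=SEED1 nimpute=25 out=Out1X". The seed is explained only by "SEED1 is a random number". SAP 9.6.2 again relies on the code "to generate 25 possible imputed datasets using PROC MI" and then adds a shift to the imputed values of MNAR cases in the active arms. The shift is set as follows: "Delta will be defined based on a percentage (10%-90%) of the mixed effect repeated measures model least-square means difference estimate at each visit". The spacing of the percentages is not given. Each analysis is "combined using PROC MIANALYZE to produce an inferential result".

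The available text contains no numeric seed, no limit on Monte Carlo error, no rule for raising the number of imputations and no check across seeds. The text of SAP 9.5 (the MNAR case list) was not available; its title gives no sign that it holds a seed.

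**The concern.** A tipping-point analysis looks for the shift at which significance is lost, so it reads p-values exactly where they lie close to the threshold. Multiple imputation adds simulation noise to each p-value, and the noise shrinks only as the number of imputations grows. If 25 leaves noise as large as the steps between deltas, part of the reported tipping delta is chance. Two analysts who follow the SAP with different seeds could then describe the robustness of the same borderline result differently. At stake is how the PANSS and CGI-S sensitivity results read, not whether the trial meets its hypotheses.

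**Working it through.** **Inputs from the documents.** 124 randomized and 93 completers per arm, about 25% discontinuation, effect size 0.48, SD of change 16.7 in one of the two planning scenarios (SAP 1.1 and 1.2); 25 imputations and deltas from 10% to 90% (SAP 9.6).

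**Assumed, because the documents do not give them.** Fraction of missing information (FMI) 0.10 to 0.30, bracketed around the 25% discontinuation; correlations between visits; delta steps of 10 percentage points. Below, the true p is the value that unlimited imputations would give.

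1. *The plan's own figure.* Expected z = 0.48 × √(93/2) = 3.27. Power = Φ(3.27 − 1.96) = 90.5% (90.3% with the t distribution). 93/0.75 = 124 per arm and 3 × 124 = 372. All reproduce.

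2. *Seed noise.* For m imputations, SD(z) ≈ √(FMI/m). The 95% range of p across seeds at a true p of 0.05 follows from z = 1.96 ± 1.96 × SD(z).

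| FMI | SD(z), m=25 | p range, m=25 | SD(z), m=500 | p range, m=500 |
|---|---|---|---|---|
| 0.10 | 0.063 | 0.037-0.066 | 0.014 | 0.047-0.053 |
| 0.20 | 0.089 | 0.033-0.074 | 0.020 | 0.046-0.055 |
| 0.30 | 0.110 | 0.030-0.081 | 0.024 | 0.045-0.056 |

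3. *Simulation check.* The set-up was 124 per arm, baseline plus six visits, 25% monotone dropout, Week 6 SD 16.7, normal-model imputation, Week 6 ANCOVA and Rubin pooling. At m=25 and a true p of 0.05, p ranged over 0.035-0.075 (FMI 0.13) and 0.032-0.081 (FMI 0.18). In three further simulated datasets (FMI 0.15-0.19) the SD of z was 0.081, 0.119 and 0.096 at m=25, and 0.018, 0.021 and 0.023 at m=500. The formula is slightly low because it ignores noise in the estimated between-imputation variance.

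4. *Chance of landing on the other side of 0.05 at m=25* (simulated, FMI 0.13-0.18): 17-23% if the true p is 0.04, 1-3% if 0.03, and 0.1% or less if 0.02. For a true p of 0.04 it falls to about 2-5% at m=100 and about 0% at m=500.

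5. *Noise against one delta step.* If all 25% of active-arm discontinuations were shifted, an upper bound, one 10-point step moves z by about 0.1 × 0.25 × z, ignoring changes in the standard error. That is 0.1 × 0.25 × 2.17 = 0.054 when the unshifted p is 0.03. A seed SD of 0.06-0.11 is therefore one to two steps.

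6. *Tipping point over 200 seeds.* The unshifted true p was set to 0.03, FMI was 0.17-0.25, and every active-arm dropout was shifted (30% of the arm in the simulated data). At m=25 the tipping delta ran from 0% to 80% of the LS mean difference. At m=500 it stayed within 20-50%, with over 95% of seeds at 30% or 40%. A value of 0% means that the unshifted imputation analysis already gave p ≥ 0.05; this happened in 4, 11 and 15 of 200 seeds (2%, 5.5% and 7.5%) for assumed correlations of 0.85, 0.75 and 0.6.

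**The case against.** The strongest reply is that little rests on these analyses. SAP 5.9.2 and 5.10.2 test the primary and key secondary endpoints by MMRM under MAR without imputation, and SAP 5.11 lists imputation only under sensitivity analysis. This stands. A reader might infer that trial success could turn on the seed; the documents do not support that.

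Second, borderline results may be uncommon. If all 25% were shifted, the largest delta would cut the effect by 0.9 × 25% = 22.5%, so significance could be lost on the grid only from a starting z below 1.96/0.775 = 2.53. At the planned z of 3.27, about Φ(3.27 − 2.53) = 77% of trials would never cross 0.05 at any planned delta (variance changes ignored). This stands too, though a smaller true effect would make borderline results more common.

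Third, the SAP states no 0.05 pass rule for sensitivity analyses. That is correct, but a tipping point implies such a threshold.

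Fourth, a reader might infer from the open seed that results could be re-run after unblinding until they look better. The documents give no ground for this. SEED1 is a placeholder in illustrative core code, the call passes an explicit seed, and SAP 9.4 requires verification by independent programming. Verification does not fix the seed in advance, but a missing value is only a gap in specification.

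Finally, a reader might suppose that fresh imputations are drawn at each delta, adding more noise. SAP 9.6.2 imputes first and then shifts those same datasets, so this is already handled.

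**Conclusion.** The point holds for the sensitivity analyses only. With 25 imputations, the seed-to-seed SD of the pooled z is about 0.06-0.11 for an assumed FMI of 0.10-0.30. A sensitivity p-value of 0.05 can read about 0.03-0.08, and a tipping delta can move by one or more steps. True p-values of roughly 0.03-0.08 are exposed; at 0.02 or below the result is practically stable.

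The size rests on the assumed FMI, visit correlations and 10-point delta spacing. The tipping-point simulation is an upper-end case, because it shifts every active-arm dropout while SAP 5.9.3.2 shifts only the MNAR pattern. This is a cheap improvement to the plan; it is not a flaw in the confirmatory tests.

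**What to change.** - In SAP 5.9.3.2, 9.6.1 and 9.6.2, raise the number of imputations until the Monte Carlo error of the pooled p-value is negligible near 0.05. The value 500 is one adequate choice (SD of z about 0.02), not a derived requirement; 100 already removes most of the problem.
- Replace SEED1 in SAP 9.6.1 with a numeric value, written in before unblinding. A fixed seed makes the result reproducible but does not reduce the noise, so both changes are needed.
- Report the Monte Carlo error of the pooled estimate and p-value with each imputation analysis.

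The cost is run time only. With one MAR analysis and nine deltas (assuming 10-point steps), 500 imputations mean 10 × 500 = 5,000 model fits per endpoint, against 10 × 25 = 250 now.

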6. To address ICE of trial or treatment discontinuation with no outcome data collected post discontinuation, the primary analysis of MMRM described above will be followed by pattern mixture model (PMM) approach with varying level of shift parameters for missing values due to discontinuations that are potentially missing not at random (MNAR), including discontinuation due to lack of efficacy or due to adverse events. This will be implemented using delta adjustment imputation method. Further details will be described in the statistical analysis plan (SAP).

The statistical hypothesis testing on the primary endpoint (emraclidine 30 mg QD vs placebo and emraclidine 15 mg QD vs placebo) will be based on the estimated treatment difference from the model at Week 6 and will be tested in a hierarchical order with each at 2-sided alpha level 0.05. The evaluation of other time points will also be derived from the same model.

The number and proportion of responders (ie, participants with 30% reduction from Baseline in the PANSS total score at Week 6 or the last assessment before discontinuation) will be summarized. A logistic regression model, with baseline PANSS as a covariate, will be used to compare the proportion of responders in each active arm with placebo. If expected counts are <5, then a Fisher's Exact test will be used.

The secondary estimand has the following attributes:

1. Treatments as randomized
2. mITT population as the primary population of interest
3. Change from Baseline to Week 6 in CGI-S score as the endpoint of interest
4. The population level summary of interest is the treatment differences estimated based on the least square mean and the corresponding 95% confidence interval from the MMRM model with treatment, visit, and treatment by visit interaction as fixed effect, participant as a random effect, and baseline CGI-S score as a covariate. An unstructured covariance structure will be used for the repeated measures. If the unstructured covariance matrix results in convergence issue, the heterogeneous Toeplitz covariance structure followed by the heterogeneous first-order autoregressive (AR(1)) structure will be used. When a reduced covariance matrix is used, the sandwich variance estimator will be used. The Kenward-Roger approximation will be used to estimate the denominator degrees of freedom.
5. ICEs will be addressed using the same strategies as described above for the primary endpoint.

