## 1.2. Sample Size Considerations

A sample size of approximately 93 subjects in each treatment group completing the Week 6 assessments (approximately 279 in total) should provide at least 90% power to detect an effect size of 0.48 in change from Baseline in the Positive and Negative Symptom Score (PANSS) total score at Week 6 between either active treatment group versus placebo at the  $\alpha=0.05$  level. The effect size of 0.48 represents a clinically meaningful effect on symptom reduction based on large scale meta-analysis of historical data from several currently approved antipsychotic medications in common usage ([Leucht et al, 2013](#)). It could be translated into a difference of 7 points versus placebo if the standard deviation of change from baseline is 14.6 points or a difference of 8 points versus placebo if the standard deviation of change from baseline is 16.7 points. Both scenarios of the standard deviation are consistent with historical observations. To account for a discontinuation rate of approximately 25% for a 6-week treatment period (as observed in Trial CVL-231-SCH-001), it is planned to randomize approximately 372 subjects.

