## 5.5. Strata and Covariates

Randomization was stratified by geographic region with two strata: United States or Other Countries.

The baseline value of each efficacy variable will be included as a covariate in the efficacy analyses.

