### **5.9.2. Main Analytical Approach**

The change from baseline to each study visit in total PANSS score will be summarized by visit and treatment group. A MMRM analysis will be used to analyze the data from all post-randomization timepoints up to Week 6 with treatment, geographic region, visit, and treatment by visit interaction as fixed effect, subject as a random effect, and baseline PANSS score as a covariate. An unstructured covariance structure will be used for the repeated measures. If the unstructured covariance matrix results in convergence issue, the heterogeneous Toeplitz covariance structure followed by the heterogeneous first-order autoregressive (AR(1)) structure will be used. The Kenward-Roger approximation will be used to estimate the denominator degrees of freedom. The difference between each emraclidine dose group and placebo at Week 6 will be estimated based on the Least Squares Mean (LSMean) difference between the treatment groups at Week 6 from the MMRM with the associated 95% confidence interval (CI) and P-value. A Cohen's D value will be derived as the ratio of the estimated difference to the population standard deviation at each visit estimated from the model (the square root of the diagonal elements of the estimated covariance matrix). The missing values are assumed to be missing at random for the main analysis, including missing due to missed visits or early termination due to COVID-19 control measures. The LSM ( $\pm$ SE) from the model will be plotted for change in PANSS total score by visit and treatment group. Similarly, the mean ( $\pm$ SD) of absolute values and change from Baseline PANSS total score will be presented by visit and treatment group.

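### The SAP's imputation model omits geographic region, so the multiple-imputation and tipping-point estimates can be slightly biased under specific conditions; adding a 0/1 region indicator costs essentially nothing

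*SAP*

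**What the plan says.** SAP Section 9.6.1 gives the imputation code. Its variable list is "var TRT Y0 Y1 Y2 ... Yn", where TRT indicates treatment, Y0 is the baseline score and the other Y terms are the scores at each visit. Twenty-five datasets are generated. Neither Section 9.6.1 nor Section 5.9.3.2 adds region.

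Each completed dataset is then analysed with the Section 5.9.2 MMRM, specified "with treatment, geographic region, visit, and treatment by visit interaction as fixed effect" and with baseline PANSS as covariate. Region is the only stratification factor: "Randomization was stratified by geographic region with two strata: United States or Other Countries" (SAP Section 5.5). Section 9.6.2 builds the tipping-point analysis on the same imputations, and Section 5.10.3 carries both analyses over to CGI-S.

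The MMRM in Protocol Section 9.3.2 has no region term. The SAP put region into the PANSS, CGI-S and responder models but not into the imputation.

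**The concern.** An imputation model should normally contain every variable in the analysis model, the randomization stratum included. Here a US and a non-US participant with the same treatment code and the same observed scores have their missing Week 6 values drawn from one common distribution, even if region still matters at that point. If the participants who drop out have a different regional mix from those who stay, and that difference is not the same in each arm, the imputed arm means move by different amounts and the treatment difference moves with them.

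At stake is how the sensitivity analyses are read. The multiple-imputation analysis is the missing-at-random check on the primary result, and the tipping point measures how far that result can be pushed. Both would carry an avoidable error from the imputation model.

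**Working it through.** **1. The plan's own figures.** SAP Section 1.2 says the sample "should provide at least 90% power to detect an effect size of 0.48", with "approximately 93 subjects in each treatment group completing the Week 6 assessments" and "a discontinuation rate of approximately 25% for a 6-week treatment period".
- n per arm = 2(1.960 + 1.282)² / 0.48² = 91.2, so 92. Power with 93 per arm is 0.905 (0.903 by the noncentral t).
- 93 / (1 − 0.25) = 124, and 3 × 124 = 372. The plan's figure is reproduced.
- The simulations use "a difference of 8 points versus placebo if the standard deviation of change from baseline is 16.7 points": 8 / 16.7 = 0.479.

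**2. What must be assumed.** The documents give no regional effect on PANSS, no US share, and no dropout by region or arm. Assumed: a 50/50 regional split, visit correlation 0.8^lag, a region effect of 0 to 12 points at Week 6, monotone dropout in the patterns shown, and equal effects in the two active arms so that only the region omission is tested. Imputation was by sequential normal regression, which for monotone dropout is equivalent to the multivariate-normal method. Week 6 change was then analysed by ANCOVA on treatment, baseline and region.

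**3. Large-sample bias with region omitted.** 300,000 per arm, true difference −8, noise about ±0.05, region effect 5 points. Dropout is shown as other countries/US.

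| Dropout pattern | Builds over 6 weeks | Constant from Week 1 | Week 6 only |
|---|---|---|---|
| Placebo 25/35, active 20/20 | 0.06 | 0.05 | 0.16 |
| Placebo 15/35, active 25/25 | 0.17 | 0.07 | 0.36 |
| Placebo 15/35, active 35/15 | 0.40 | 0.16 | 0.71 |

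- With no region effect, bias is about zero under every pattern, including those where dropout differs by region and arm.
- With dropout differing by region only (15/35 in all arms) or by arm only (35% against 20%), bias is about zero at every region effect tested.
- The most extreme case tested (12 points, Week 6 only, crossed dropout) gave 1.6.
- With region added, bias was within about 0.06 of zero everywhere.

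The smallest entries, 0.05 and 0.06, cannot be told apart from noise. The sign depends on which region does worse and where dropout concentrates.

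**4. Cost at the trial's size.** 124 per arm, 25 imputations, 400 replicates, no region effect: mean standard error 2.048 with region and 2.046 without. These runs are too noisy to measure bias (Monte Carlo error about 0.10): with no region effect, where neither version is biased, their means still differed by 0.28 (−8.18 against −7.90). The bias figures therefore rest on step 3. Relative to the standard error, 0.40 / 2.05 = 0.20 and 0.71 / 2.05 = 0.35.

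**5. Size on the tipping-point scale.** Delta runs from 10% to 90% of the MMRM difference. If that difference is 8 points and all of a 25% active-arm dropout counts as MNAR, each 10-percentage-point step moves the estimate by 0.10 × 8 × 0.25 = 0.20 points. A bias of 0.17 to 0.40 is then roughly one to two steps.

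**6. Comparison with the MMRM.** 60,000 per arm, 50% US, region effect 6 points, dropout (other/US) 10/40 on active and 25/25 on placebo; all assumed; noise about 0.1; the same data for all three methods; true difference −8.

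| Region effect | MMRM as in 5.9.2 | MI without region | MI with region |
|---|---|---|---|
| Builds over 6 weeks | −8.38 | −8.42 | −8.07 |
| Week 6 only | −8.46 | −8.48 | −7.86 |
| Constant from Week 1 | −8.02 | −8.17 | −7.99 |

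Section 5.9.2 has region as a main effect with no region-by-visit term, so it cannot represent a regional effect that grows over time. An imputation model that includes region can, because it relates region to each visit's score separately.

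**The case against.** The strongest case against the point is that little depends on it. The four hypotheses are tested by the direct MMRM, and the imputations feed sensitivity analyses only. Every mITT participant has a baseline and at least one post-baseline PANSS, and those scores already carry part of any regional difference; the constant-effect column shows how much that helps. The region effects and crossed dropout patterns are assumptions chosen to expose the mechanism. All of this stands, and it limits the point to a minor improvement. It could also be said that Section 9.6 gives core code only, so the final program may differ. But Section 9.6.1 says this is the code to be used, and no text commits to adding region.

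A reader might infer more than the documents support:
- *Dropout that differs by region and arm is enough to cause bias.* It is not. Without a region effect beyond the observed scores, bias is zero.
- *The omission produces a gap between MMRM and MI that would be misread as sensitivity to missing data.* Mostly it does not. Where the omission matters most, the two agree within 0.04 because the MMRM shares the bias. A gap due to the omission appears only for a constant effect, and it is about 0.15.
- *The imputation rests on a weaker missing-at-random assumption.* Conditioning on fewer variables generally makes the assumption more restrictive.
- *The trial stratifies because placebo response or dropout differs by region.* Neither document gives a reason for the stratification.

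**Conclusion.** The mismatch is real: the imputation model lacks a stratum that the analysis model contains, and the tipping-point analysis inherits it. The consequence is conditional and small. Under assumed region effects of 5 to 6 points, the bias on an 8-point difference is about 0.05 to 0.4 points in the more plausible scenarios. It reaches about 0.7 if the effect appears only at Week 6, and it is zero if region is not prognostic given the observed scores or if the regional dropout pattern is the same in all arms. It could move a reported tipping point by a step or two, in either direction. The primary test, the sample size and the power are not affected by this omission. That the primary MMRM can itself be biased when a regional effect grows over time is a separate property of the Section 5.9.2 model, and changing the imputation does not alter it.

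**What to change.** Before unblinding, add a numeric 0/1 US/other indicator to the variable list in SAP Section 9.6.1, and state in Section 5.9.3.2 that the imputation model contains every variable in the Section 5.9.2 model. Region is known for everyone at randomization, so it is never itself imputed. The cost is one variable in one line, with no change in sample size, power, primary test or, to any visible degree, standard error.

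Add a sentence on interpretation. If the regional effect grows over time, the corrected imputation is less biased than the MMRM, and the two could then differ by about 0.3 (−8.38 against −8.07) to 0.6 (−8.46 against −7.86) under the assumptions in step 6. Such a difference would point to the missing region-by-visit term and should not be read as sensitivity to missing data.

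Two related matters can be settled in the same edit. TRT is described with two character values, which pools the two doses although they are tested separately, and it needs numeric coding. The protocol and SAP versions of the MMRM also differ on whether region is included and should be reconciled.
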